2.2 Participants' characteristics

The Clinical study will be performed in 3 Clinical Centers: University of Patras (UoP), Greece; INSERM-Nancy, France; and MATERIA- Nicosia, Cyprus. Each Center will recruit 170 individuals for the FrailSafe study. By this way a total of 510 community living subjects aged 70 years and older will be recruited. The inclusion and non-inclusion criteria are demonstrated in table 1.

Table 1. Inclusion and exclusion criteria

Inclusion criteria
Age ≥70 years
Informed consent provided
Exclusion criteria
Lack of wish to participate
Consent withheld
Inability to give consent because of incapacity
Inability to walk
Inability to speak Greek or French (see clinical centers)
Diagnosis of clinically significant cognitive impairment or score less than 24 on the Mini– Mental State Examination
Diagnosis of advanced malignancy, other terminal illness or an estimated life expectancy of less than 12 months
Active psychiatric disorder based on medical records or clinical opinion at the time of recruitment, current substance users, or excessive alcohol drinkers.

The numerical threshold for "older age" has always been controversial, though most widely accepted was the age of 65 years, corresponding in the usual age of retirement. Still, nowadays "young old" individuals maintain a good general health condition and with the exception of special cases, frailty is most likely to be encountered in older age ranges. In the FrailSafe study, since we need to include people in non-frail, pre-frail, as well as frail conditions, it was decided that the age threshold will be that of 70 years.

In order to be able to comply better with the requirements of the study (usage of technical material, cooperation for the testing of novel equipment, need for participant's feedback and relatively long follow up period), subjects with highly debilitating conditions, such as inability to walk, presence of clinically significant cognitive impairment, or active psychiatric

disorder will be excluded from the study. Similarly, subjects with serious medical conditions that convey a guarded prognosis (estimated life expectancy of less than 12 months) will be excluded as well.

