2.3 Groups

All participants will be given a unique number by the time they are allocated in four groups (table 2), with the addition of the code number of each centre in front: (1 for Patras, 2 for Cyprus and 3 for Nancy). For each centre, participants with numbers 001 to 080 will belong to the Start Up Group (A), the 40 following will belong to the Main Group (B), the 25 following afterwards will belong to the Evaluation Group (C) and the last 25 to the Control Group (D). The Evaluation Group (C) will be further divided in two parts: participants with numbers 121-140 will belong to the "standard" Evaluation Group; while those with numbers 141-145 will belong to the Long Term Evaluation Group, with an augmented intensity of following up.

Group	Serial Number
A- Start Up	001-080
B- Main	081-120
C- Evaluation	121-145
Ci- Standard Evaluation	121-140
Cii- Long term Evaluation	141-145
D- Control	146-170
With the prefix of the centre number	1 for Patras, Greece
	2 for Nicosia, Cyprus
	3 for Nancy, France

Table 2. Participants' ID numbers

In case of exclusion or premature withdrawal of a participant, (s)he has been replaced by a new subject, to whom a new unique ID number has been given. The substitute subjects were given the number of the individual they have replaced with the addition of 500. For example, if the participant number 1094 withdrew from the study (subject number 94 from the first recruitment centre), the subject that replaced him/her will take the number 1594

(=1094+500). For subject number 3164 who withdrew (participant number 164 from the third recruitment centre), the subject replacing him/her will take the number 3664 (=3164+500). However, participants' replacements took place only until M19. Any subject that dropped off after July 2017, has not been and will not be replaced due to lack of time for catching up with the minimum follow up time period required (M19 represents the middle timeline of the project).

The number of the participants allocated in each group is already agreed in the original proposal and corresponds mostly to issues of availability of material and workforce in the context of actual financial potential and less to pure mathematical calculations, due to the originality of the project and the absence of a previous reference to consider for sample size calculations.

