2.4 Sampling, recruitment procedure and randomization

The method of sampling from the general population will be the convenient method, in order to create a pool of candidate participants. Although it might not be the most unbiased method of recruitment, it is the most suitable for the present study mainly because our participants are actually volunteers. We addressed to them, in their natural environment (community settings, their own home) in order to ask them to voluntarily participate in the FrailSafe project.

The recruitment strategy will be organized by each one of the 3 centres individually. Main procedures that were followed are collaborations with older people's associations and public events in order to inform people about the importance of intervening on frailty and the objectives of FrailSafe study. More specifically, we approached medical institutions and rehabilitation centers, public organizations and local societies/associations, home care services, older people's and relatives' focus groups and individuals occupied with health care provision. In parallel, a communication policy by advertising in the mass media was attempted (local television channels, newspapers and websites), with very satisfying results.

The aforementioned strategy aims not only at attracting interested individuals eligible for the study, but also at spreading the word in people who are not necessarily eligible, but who could mobilize their friends and relatives and inform their personal or professional environment.

Inevitably, a certain degree of motivation bias is inherited in this project, and cannot be fully excluded. Potential participants in all centers were asked to participate after explaining the study procedures in details. Individuals who were not motivated declined to consent. To overcome, as much as possible, this issue was stressed the future benefits of the study, as well as the activities and interaction during the study that may spice up the daily routine.

Despite the overall common procedures, different enrollment strategies were somehow proved to be more effective in each clinical center. For instance, INSERM (France) mainly carried out public targeted meetings inviting older people to participate, whereas in Patras (Greece) the local Geriatric and Gerontology Society mainly invited its members to participate, and similarly MATERIA (Cyprus). Therefore in the whole, the study sample was not made only by self-volunteered participants.

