By this extrovert approach a pool of interested individuals is created and eligible participants (subjects who seemingly fulfil the inclusion and non-inclusion criteria) are been called by telephone to make a first appointment.

During this first meeting the individual are thoroughly informed (information letter and supplementary oral information), questions are answered and, in case of agreement, an informed consent is signed. Data regarding social interaction and natural language analysis is collected. A first clinical evaluation follows (part of the clinical evaluation battery-section 3.1) in order to investigate the Fried's criteria of frailty, comorbidities and cognitive status (tables 6, 9 and 13). This information is necessary for:

- The classification into frailty categories. The participants will be classified in three groups according to their frailty status assessed by the criteria of Fried's frailty index (1) (table 9). Individuals with 3 or more criteria will be allocated in the frailty category, those with 1-2 criteria will be characterized as pre-frail, while those with no frailty criterion will be characterized non frail.
- Identification of leader co-morbidities: history of stroke, mild cognitive impairment (MCI), osteoarthritis for men and osteoporosis for women.
- The verification of inclusion and non-inclusion criteria. In case of exclusion, replacement of the participant with another subject will take place. For this reason the pool of our candidate participants should be considerably larger than the number of subjects that actually need to be recruited.

The proportion of subgroups ("non-frails", "pre-frails", and "frails") according to the Fried's frailty criteria was changed from the initial 2:1:1, i.e. non-frail (50%): pre-frail (25%): and frail (25%), to 1.5 : 1.5 : 1 for groups A and B added up together.

This proportion is more favorable and exploitable due to the following reasons:

- We considered the risk that there will not be enough users to achieve project's objectives related to frailty itself as pointed out by the experts in the 1st review of Frailsafe (see recommendations FR1 and FR2). The project focuses mostly on non-frail and pre-frail people since the frail group does not offer much in monitoring the transition between states.

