- Non-frail and mostly pre-frail individuals are more likely to benefit from interventions in terms of prevention of evolution of their frailty status (MO3), than the already frail ones that are less likely to regress to a previous frailty status.
- Especially the pre-frail individuals, that outweigh other categories in our population, are those who are traditionally considered to benefit more from potential interventions and thus are generally the target of the standard CGA (ie, excluding patients who are either too well or are too sick to derive benefit) (MO4) (1). If the

FrailSafe system is to be tested for its added value on the standard CGA (main medical objective), pre-frail individuals should be the dominant target group.

- Our study focuses on prevention (MO6), therefore, a smaller number of already frail people should be allowed. However, they should also exist in our study population in order to enable us to make comparisons and draw conclusions.
- From the very first analysis that has been performed and presented in D2.6 Behavioral management, we observe that the pre-frail category almost constantly scores in between the performances of the non-frail and the frail group in all tests and parameters. This emphasizes the fact that they constitute a dynamic intermediate category with the potential to approach either the one or the other extreme (MO5). Thus, the results of potential interventions could be measurable and could contribute to the prevention of category shifting towards frailty.
- Under the prism of a potential exploitation of the FrailSafe end product in the future, individuals, health care professionals, insurance companies and health policy makers could be more interested to apply the integrated FrailSafe system in people that are already threatened by a devastating health condition such as frailty (ie the pre-frails), rather than devoting resources in a totally healthy population, who might not be eligible for reimbursable health interventions. Therefore this frailty category is considered to be of great interest for the FrailSafe project (MO7).

The above listed proportions are calculated on the total of participants, in the sum from all three centers, so different percentages may be present within groups from Cyprus, Greece and France. However, the same criteria (Fried's)(2) (table 9) will be applied in all clinical centers.

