This stratification of frailty according to Fried's criteria will not be used in the analysis of data. The study population will be considered as a whole, from which new frailty metrics will be identified using both hard and proxy outcomes; the latter will be based on the change of clinical and FrailSafe parameters.

The sample in this study should ideally be randomly selected from the general population in those aged \geq 70 years. This would require a larger number of participants and a larger number of study workforce, as well as equipment, in order to include individuals with the right case mix of frailty levels and a representative number of comorbidities. Undoubtedly, such a design would have been preferred and would have provided strong and reliable clinical results. However, current financial resources in this Horizon 2020 call, which are split among technological development and clinical evaluation, were not sufficient for this type of methodology.

It is understandable that transition among the groups as defined by Fried's criteria might not be easily observed with the current study design, as number of participants, time span and number of simultaneous FrailSafe assessments are limited. On the other hand, functional changes or proxy outcomes expressing loss of functional reserve is likely to be detected when the study group is examined as a whole. The choice of the current clinical study methodology was a compromise between an ideal approach and a more practical solution, though hampered by numerous limitations.

In addition, in each of the three frailty status, at least 7 have prior stroke, 7 MCI (Mild Cognitive Impairment), 7 either osteoporosis for women or osteoarthritis for men and 7 nothing of the mentioned above. There is no particular concern in which group they will

belong. If this will not be achieved by randomization, the investigator, who will be in charge to overall monitor randomization, will intervene to further randomly stratify cases to obtain this pre-specified study objective.

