3.7.8 FrailSafe system's application standardization

As predicted by the initial proposal and its amendments, not the totality of the FrailSafe system devices was available since the beginning of the clinical study.

Therefore, we noted a quite important heterogeneity among the first FrailSafe sessions conducted in the centres of Patras and Cyprus. In order to address this source of bias, the

very first participants for whom the FrailSafe session was incomplete according to some minimum requirements (enlisted bellow), will be called back in order to repeat the session.

The FraiSafe system devices which are currently available and are going to be used in all FraiISafe sessions (=home visits), from now until new versions of devices arrive, are:

- The tablets with virtual reality games (for all participants)
- The smartphones with the GPS application (for all participants)
- The blood pressure monitoring devices (for all participants)
- The WWS devices (strap version) (for 1 participant at a time)
- The dynamometers for grip strength games' playing (for all participants)
- The beacons (for all participants).

Towards the direction of standardizing the procedures and adapting the material to the actual needs of the participants, working documents treating practical issues such as study's material, anticipated and actually occurring problems and procedures have been generated and are being constantly updated. Similarly, detailed check lists about the material, requirements and conditions to be verified before, during and after the clinical evaluation and the FrailSafe home visits have been distributed in the 3 clinical centres (Annex 19).

4. Operational procedures per group

In a more concentrated and systematic way the operational procedures per group are as following:

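### Frailty metrics are to be derived from the pooled three-centre sample, and no centre or language term is named, although frailty mix, recruitment and language can all differ by centre

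*Protocol*

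**What the plan says.** Section 2.2 sets equal enrolment: "Each Center will recruit 170 individuals for the FrailSafe study", giving "a total of 510 community living subjects aged 70 years and older will be recruited". The eligibility table there admits speakers of Greek or French, depending on the centre.

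Section 2.4 sets the frailty ratio, changed "to 1.5 : 1.5 : 1 for groups A and B added up together", on the sum of the three centres, "so different percentages may be present within groups from Cyprus, Greece and France". On recruitment it reports that "different enrollment strategies were somehow proved to be more effective in each clinical center": mainly targeted public meetings in France, and mainly invitations to members of a local geriatric society in Patras, with a similar route in Cyprus. It then drops the Fried categories from the analysis and continues: "The study population will be considered as a whole". New metrics are to be found from that population.

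Section 2.6 records a late start in Nancy. Section 3.7.8 adds that "we noted a quite important heterogeneity among the first FrailSafe sessions conducted in the centres of Patras and Cyprus". Section 3.2.1 compares each text sample with others by cosine distance and scores it for entropy, sentiment and syntax. Natural language analysis enters the Clinical Frailty Index (CIFI) in two domains (Appendix I).

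Sections 5.2.2 and 5.4 plan correlations of FrailSafe variables with the proxy variables, clustering, dimension reduction, ReliefF ranking and Cox models. None of these names centre or language.

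**The concern.** A variable that is tied both to frailty level and to how a metric is recorded is a confounder. Centre can be one here. The frailty mix is free to vary by centre, recruitment routes differ, and language follows the centre. In pooled data, a metric with no relation to frailty inside any centre can then still correlate with frailty across the whole sample. It may be ranked highly by feature selection or help to define a cluster that is in fact a centre or a language.

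Text features are the plainest case. A cosine distance between a French and a Greek sample measures language before it measures cognition, and the result feeds a frailty index. A biomarker meant for wide use should not turn out to be a marker of where the participant was recruited.

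**Working it through.** **Inputs from the protocol.** Each centre has 80 (A) + 40 (B) + 25 (C) + 25 (D) = 170, and 3 × 170 = 510, which reproduces the stated total. There is no power figure to reproduce: Section 2.3 says the group sizes owe "less to pure mathematical calculations" than to resources. Group D receives no FrailSafe system (Section 2.5), so at most 510 − 75 = 435 people can have a FrailSafe metric. Groups A and B give 3 × 120 = 360. The target ratio makes 25% of A + B frail, that is 90 of 360.

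**Assumptions.** The protocol gives no frailty mix by centre and no size for a centre shift in any metric. Both are assumed below. In every case frailty and the metric are unrelated within each centre.

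**Check 1, closed form.** Frailty means by centre are −a, 0, +a and metric means are −d, 0, +d, in within-centre SD units, with equal centres. The between-centre covariance is 2ad/3 and the between-centre variances are 2a²/3 and 2d²/3. The pooled correlation is

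r = (2ad/3) / √[(1 + 2a²/3)(1 + 2d²/3)].

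The false-positive rate is the probability that a normal variable with mean atanh(r)·√(n − 3) and unit variance lies beyond ±1.96.

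Example with a = 0.4, d = 0.5: r = 0.1333 / √(1.1067 × 1.1667) = 0.117. At n = 435 the mean is 2.45, and the rate is about 69%.

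| a | d | r | n = 435 (A–C) | n = 360 (A+B) |
|---|---|---|---|---|
| 0.4 | 0.3 | 0.074 | 34% | 29% |
| 0.4 | 0.5 | 0.117 | 69% | 61% |
| 0.4 | 0.7 | 0.154 | 90% | 84% |
| 0.2 | 0.3 | 0.038 | 13% | 11% |
| 0.2 | 0.5 | 0.061 | 25% | 21% |
| 0.2 | 0.7 | 0.080 | 38% | 33% |

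**Check 2, simulation on frail shares.** 360 people, 120 per centre, 2,000 runs per scenario, two-sided 5% test of the Pearson correlation between frail status and the metric. The shares average the stated 25%. Frail status stands in for frailty level.

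| Frail share by centre | Metric shift 0/0.25/0.5 SD | Metric shift 0/0.5/1.0 SD |
|---|---|---|
| 25/25/25% | 5.2% | 5.0% |
| 20/25/30% | 6.8% | 9.7% |
| 15/25/35% | 10.5% | 28.2% |
| 10/25/40% | 19.5% | 53.5% |

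With no metric shift, the pooled rate was 4.6% to 5.7% whatever the mix. After centring both variables by centre, it was 4.3% to 5.9% in all scenarios.

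**What the checks show.** The inflation needs both a mix difference and a metric shift. If either is absent, pooling does no harm to the error rate.

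**The case against.** A reader might infer from "The study population will be considered as a whole" that the protocol has decided to ignore centre. The text does not support that. The preceding sentence sets aside the Fried categories, and the contrast is with those categories.

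Without that reading, what remains is an omission. Centre terms are commonly left to a statistical analysis plan, which is not at hand, and centre is the first digit of every participant ID, so nothing prevents adjustment. This has force: silence alone proves no error. But the protocol itself allows the imbalance, pools the population to find metrics and sets out its methods in Section 5. It also names other factors to account for, comorbidities in Section 2.4 and sex for IADL in Section 3.1.9. Stating how centre and language are handled belongs beside these.

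The centre differences can also be overstated. The mix is said only to be possibly different. The enrolment text starts from common procedures, and the same Fried criteria apply everywhere. The device heterogeneity concerns first sessions, and incomplete ones are to be repeated with a common minimum set. Nancy is reported to have caught up (Section 2.6). These steps reduce the timing and device differences but leave language and recruitment route as they were.

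A reader might also suppose that C versus D is confounded by centre. It is not: each centre contributes 25 to each group. The most a centre term can add there is precision. Constant centre offsets also cancel in within-person change, so change-based proxy outcomes are less exposed than level-based scores.

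**Conclusion.** The point holds as a conditional risk to level-based results: correlations, clusters, feature rankings, CIFI and Technical Frailty Index (TFI) scores, and Cox models that use them. It is no demonstrated bias, since the protocol quantifies neither of the two shifts that are needed. Over the assumed ranges, the pooled false-positive rate runs from about 7% (frail shares 20/25/30%, metric shift up to 0.5 SD) to about 90% (±0.4 SD and ±0.7 SD, n = 435). A centre term restores about 5%. The text features of the CIFI are the most exposed, because language differs by design and comparisons across samples are planned. The change is worth making because the data needed are already collected.

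**What to change.** Keep the decision not to use Fried strata. Add to Section 5:

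- Association and survival models include centre as a fixed effect or as a stratum.
- Text features are computed and compared within language only, before they enter the CIFI or any clustering.
- Frailty signatures and prediction models are checked by leaving out one centre at a time (with groups A to C, fitting on 290 and testing on 145).
- Cluster results may be reported with and without centring by centre as a sensitivity analysis. Centring should not be the only version, because it can remove real frailty differences between centres.

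For C versus D a centre term is optional and serves precision only.

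The cost is two degrees of freedom per model with a fixed centre effect and some extra analysis work. No new data are needed.

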2.5 Time schedule

All individuals with numbers 1-146 (groups A to C) will undergo the main evaluations, assessments and interventions and a blood sampling in the beginning of the study. Differences among groups concern the timing and the frequency of these interventions (figure 1). The last 25 participants (control group) will not test the FrailSafe system, but will receive two clinical evaluations, one blood taking and one telephone follow up interview. For all participants, data regarding social interaction and natural language analysis will be collected by their entry to the study. Data collection of written text will be repeated in the context of each clinical evaluation session.

[figure not shown]

Figure 1. FrailSafe study's time schedule per group and per center

In each clinical center the procedures followed are:

Eighty participants of group A were supposed to undergo a clinical evaluation, a blood sampling and a FrailSafe system instauration at the time of their recruitment (\geq M6). However, the FrailSafe home visit, along with the blood drawing which accompanies it, was not possible to be done on time for all participants of group A. The reasons for this, along with a proposed mitigation strategy are described below (section 2.6). The second clinical evaluation session and FrailSafe system utilization is scheduled for M26 and a last clinical evaluation will take place in M33. Meanwhile, in 3 months intervals, there is the telephone follow up questionnaire up until M36, unless it coincides with a clinical evaluation or a FrailSafe home visit session, where it will be administered in person and not by telephone. A second blood sampling will take place in M27 only for a subgroup of participants in the clinical center of Patras' University.

The participants of group B (40 subjects) started in M10 by the clinical evaluation session. Similarly as in group A, and mainly because of the delay in this first group, the first FrailSafe system installation for group B, along with the blood taking that accompanies it, is not yet completed. The proposed mitigation strategy is described below (section 2.6). In this group the FrailSafe system application will be more intensive, every two or three (only for the first sessions) months, from M12 to M27, for a total of 7 times. The second and third clinical evaluation sessions will take place in M16 and M22 respectively. Finally, a last clinical evaluation session with take place in M35. Telephone follow up assessments will be done every 3 months' time from M26 to M36, but the follow up questionnaire will be administered in person in every FrailSafe home visit also from M12 to M22, during the corresponding appointments. In practice, group B due to its frequent FrailSafe home visits will receive no more than 2 follow up phone calls (M29 and M32). A second blood sampling will take place in M25 only for a subgroup of participants in the clinical center of Patras' University.

The group C will be the group to test the FrailSafe system in its integrity as it will be developed by the interactions and adaptations from the previous groups' experience. Starting in M31 the triplet clinical evaluation, blood sampling and FrailSafe system will be applied. Twenty of the participants in this group will have the FrailSafe system for 5 days (as used by the other groups also), 3 times in total with 2 months' intervals (M31 to M35). On the other hand, five individuals of group C will be asked to carry the FrailSafe system for 60 days in continuation. At the end of the FrailSafe system testing, a satisfaction interview will be conducted to each group C individual. All group C participants will receive a second clinical evaluation in the end of the study (M36) and a follow up questionnaire in M33 for the first arm of group C in M34 by telephone call. A second blood sampling will take place in M35 only for a subgroup of participants in the clinical center of Patras' University.

Finally the group D (control group) will receive no application of the FrailSafe system. A blood sampling will take place in the recruitment (M31), together with a clinical evaluation

session. The latter will be repeated once more at the end (M36). One telephone follow up will take place in M33.

In case of premature exit from the study of an individual due to consent withdrawal, death or occurrence of another condition rendering the participation impossible and provided that less than the 50% of the assessments scheduled were accomplished, each departing participant will be replaced by a new one. For the latter, the time schedule of the follow up planned will be shifted forward to the time line of the departing participant after starting from the basic beginning's triplet: clinical evaluation, blood sampling, FrailSafe system. In case the replacing subject also drops out of the study, no further replacement is scheduled for technical reasons.

The time schedule presented above remains a framework that it is possibly subject to adjustments according to the availability of each individual. This study aims to be the least invasive possible in terms of participants' regular life planning and activities. Under this perspective, reasonable deviations of the scale of ± 1 month should be considered acceptable.

